 - For patients in which target lesion response assessments are performed with both scans (according to RECIST 1.1) and photographs (according to Clinical Response Criteria for Externally Visible Tumors), the investigator’s response assessment will be according to Composite Response Criteria.
- Duration of response (DOR)– measured from the time measurement criteria are first met for CR/partial response (PR), whichever is recorded first, until the first date of recurrent or progressive disease or death due to any cause in patients with best overall response (BOR) of CR or PR.

- PFS – measured from time of enrollment until the first date of recurrent or progressive disease, or death due to any cause
- OS – measured from time of enrollment until death due to any cause
- CR rate
- Change in scores of patient-reported outcomes on EORTC QLQ-C30 (except Group 6)
- AEs
- Cemiplimab concentrations in serum
- Anti-drug antibodies (ADA)
- For Group 6 only: To assess relationships between PD-L1 status (by IHC) and efficacy measures (ORR, DOR, PFS).

Procedures and Assessments

Tumor imaging (computed tomography [CT] or magnetic resonance imaging [MRI]) and digital medical photography (for externally visible lesions) will be performed to measure tumor burden and to characterize the efficacy profile of study treatments using response criteria.

Physical examination, laboratory tests, vital signs, electrocardiogram (ECG), pregnancy test for women of childbearing potential, and recording of AEs and concomitant medications will be performed to ensure patient safety and to characterize the safety profiles of study treatments.

Other assessments will include:

- Peripheral blood samples for PK
- Peripheral blood samples to assess anti-cemiplimab antibodies
- Tumor biopsies
- Quality of life assessments
- [¹⁸F]-FDG PET scans (Group 4, excluding patients enrolled at sites in Germany)

Statistical Plan

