8.2.2. Secondary Endpoints

The secondary efficacy endpoints are:

- ORR for Groups 1 through 6 by investigator assessments:
 - For patients with metastatic CSCC in which all response assessments are performed on radiologic scans according to RECIST 1.1, the term “composite response assessment” is not applicable. The investigator’s response assessment for such patients will be RECIST 1.1 assessment.
 - For patients with locally advanced CSCC in which all response assessments are performed on photographs according to Clinical Response Criteria for Externally Visible Tumors (in [Appendix 2](#)), the term “composite response assessment” is not

applicable. The investigator’s response assessment for such patients will be according to Clinical Response Criteria for Externally Visible Tumors.

- For patients in which target lesion response assessments are performed with both scans (according to RECIST 1.1) and photographs (according to Clinical Response Criteria for Externally Visible Tumors), the investigator’s response assessment will be according to Composite Response Criteria (in [Appendix 3](#)).
- DOR – measured from the time measurement criteria are first met for CR/PR, whichever is recorded first, until the first date of recurrent or progressive disease or death due to any cause in patients with best overall response (BOR) of CR or PR
- PFS – measured from time of enrollment until the first date of recurrent or progressive disease, or death due to any cause
- OS – measured from time of enrollment until death due to any cause
- CR rate
- Change in scores of patient-reported outcomes on EORTC QLQ-C30 (except Group 6)
- AEs
- Cemiplimab concentrations in serum ([Appendix 3](#))
- Anti-drug antibodies (ADA)
- For Group 6 only: To assess relationships between PD-L1 status (by IHC) and efficacy measures (ORR, DOR, PFS).

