APPENDIX 10. STATISTICAL ANALYSES

ESTIMANDS

For Group 6 primary analysis, the statistical methods for the primary and secondary endpoints will be consistent with that which was done for Groups 1 to 3. This will facilitate a meaningful comparison of Group 6 with the previous groups. Additional statistical analyses will also be performed, including sensitivity analyses for DOR and PFS assuming informative censoring for intercurrent event.

Attributes for ORR per Central Review and Investigator Assessment

1. The study population is defined as CSCC patients who are enrolled on the protocol.
2. The endpoint is ORR, defined as the proportion of patients with BOR of CR or PR. ORR per central review is the primary endpoint, and ORR per investigator assessment is a secondary endpoint.
3. Intercurrent events and how to account for these events are described in [Table 16](#).
4. Estimated ORR will be provided, along with the 2-sided 95% exact binomial confidence interval using the Clopper-Pearson method.

Table 16: Intercurrent Events for Analysis of ORR per Central Review and Investigator Assessment

Intercurrent events	Rules of imputing data in primary analysis
Initiation of palliative radiation therapy	Patient will be considered to have PD at time of initiation of radiation (Section 5.7.4 of protocol).
Surgical removal of target lesion	BOR will be considered as PR if no prior PD is observed (Section 5.7.3 of protocol).
Unconventional responses (eg, a patient first experience PD and then CR or PR)	BOR will be considered as PD.
No evaluable postbaseline tumor assessment	BOR will be deemed NE. Patient with BOR of NE will be included in the ORR analysis as a non-responder.

A sensitivity analysis will be performed for ORR where the intercurrent events of “initiation of palliative radiation therapy” and “surgical removal of target lesion” will be ignored. Patients with unconventional responses will be considered as responders. Patients with BOR of NE will be excluded from this analysis.

Attributes for DOR per Central Review and Investigator Assessment

1. The study population is defined as CSCC patients who are enrolled on the protocol and had a CR/PR response.
2. The endpoint is DOR, measured from the time measurement criteria are first met for CR/PR (whichever is first recorded) until the first date of recurrent or progressive disease or death due to any cause in patients with BOR of CR or PR.

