1.2.2. Secondary Objectives

The secondary objectives for Groups 1 to 4, and Group 6 are:

- To estimate ORR according to investigator review
- To estimate the duration of response (DOR), PFS, and OS by central and investigator review
- To estimate the complete response (CR) rate by central review
- To assess the safety and tolerability of cemiplimab
- To assess the PK of cemiplimab
- To assess the immunogenicity of cemiplimab

For Groups 1 to 5 only:

- To assess the impact of cemiplimab on quality of life using European Organization for Research and Treatment of Cancer Quality of Life Questionnaire Core 30 (EORTC QLQ-C30)

Group 6 only: To assess relationships between PD-L1 status (by IHC) and efficacy measures (ORR, DOR, PFS).

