4.5.2. Secondary Efficacy Variables

ORR based on investigator-assessed evaluation is also derived from the overall response that is based on investigator-assessed evaluation at each time point at which a response assessment occurs using the RECIST version 1.1 (Appendix 1 of the protocol) or the composite response criteria (Appendix 2 of the protocol).

Duration of response (DOR) is determined for patients with best overall response of CR or PR. Duration of response is measured from the time measurement criteria are first met for CR/PR (whichever is first recorded) until the first date of recurrent or progressive disease (radiographic or photographic), or death due to any cause. DOR by central-reviewed evaluation is the key secondary endpoint.

Patients who do not have a documented tumor progression or death will be censored at the last evaluable tumor assessment.

Progression-free survival (PFS) is measured from the start of treatment until the first date of recurrent or progressive disease (radiographic or photographic), or death due to any cause. Patients who do not have a documented tumor progression or death will be censored at the last evaluable tumor assessment. If a patient has no post-baseline tumor assessment, the patient will be censored at the first treatment date.

Overall survival (OS) is measured from the start of treatment until death due to any cause. Patients who do not have a survival event will be censored at the last date that patient is documented to be alive. As many patients may receive subsequent therapy after disease progression, a variant of OS will also be defined as censoring patients who do not have a survival event at the first date of a subsequent therapy is taken.

Time to tumor response (TTR) is determined for patients with BOR of CR or PR. TTR is measured from the start of treatment until the time measurement criteria are first met for CR/PR (whichever is first recorded).

For all of the above time-to-event variables, the time to event (day) is the date of event/censor the date of first study treatment+ 1.

CR rate is determined by the proportion of patients with best overall response of CR. Patients with best overall response of NE will be considered as not reaching an objective response of CR.

Disease control rate (DCR) is determined by the proportion of patients with BOR of CR, PR, or SD.

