11. APPENDIX

11.1. Summary of Statistical Analyses

Efficacy Analysis:

Endpoint	Analysis Populations	Primary Analysis	Statistical Method	Supportive Analysis	Subgroup Analysis	Other Analyses
Primary Endpoint						
ORR	FAS	Proportion of patients with best overall response of CR or PR (central review)	95% exact binomial confidence interval using Clopper-Pearson method	Exact binomial test p-value	Yes	Yes
Secondary Endpoints						
ORR	FAS	Proportion of patients with best overall response of CR or PR (investigator review)	95% exact binomial confidence interval using Clopper-Pearson method	Exact binomial test p-value	No	No
Duration of response	Patients with best overall response of CR/PR in FAS	From the time measurement criteria are first met for CR/PR (whichever is first recorded) until the first date of recurrent or progressive disease (radiographic), or death due to any cause.	Kaplan-Meier method and descriptive statistics	No	Yes	No
Progression-free survival	FAS	From the start of treatment until the first date of recurrent or progressive disease (radiographic), or death due to any cause.	Kaplan-Meier method	No	No	No
Overall survival	FAS	From the start of treatment until death due to any cause.	Kaplan-Meier method	No	No	No
Quality of life	FAS	Changes scores from day 1 of EORTC-QLQ-C30	Descriptive statistics and longitudinal plots	No	No	No

Safety Analyses:

Endpoint	Analysis Populations	Primary Analysis	Statistical Method	Supportive Analysis	Subgroup Analysis	Other Analyses
Adverse Events	SAF	Percent of patients by system organ class and PT	Descriptive Statistics	No	No	No

Signature Page for VV-RIM-00330503 v1.0

Approval/eSignature	 12-Dec-2023 22:56:28 GMT+0000
---------------------	---

Approval/eSignature	 13-Dec-2023 02:12:18 GMT+0000
---------------------	---

Approval/eSignature	 13-Dec-2023 03:02:56 GMT+0000
---------------------	---

Signature Page for VV-RIM-00330503 v1.0 Approved

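### SAP 4.5.2 counts every time-to-event variable from first study treatment, which contradicts its own definition of duration of response

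*SAP*

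**What the plan says.** SAP Section 4.5.2 defines, in order, investigator-assessed ORR, DOR, PFS, OS and TTR. On DOR it states: "Duration of response is measured from the time measurement criteria are first met for CR/PR (whichever is first recorded"). It gives DOR an event rule (progression or death) and a censoring rule (last evaluable tumour assessment), and adds: "DOR by central-reviewed evaluation is the key secondary endpoint". PFS, OS and TTR are each defined from the start of treatment.

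After these definitions comes a single day-count rule: "For all of the above time-to-event variables, the time to event (day) is the date of event/censor the date of first study treatment+ 1". As extracted, the sentence has no operator between the two dates. A minus sign is the evident reading, and its absence is not counted as an error. The origin, first study treatment, is named in words.

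The other definitions of DOR agree with one another:

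- SAP 11.1, summary table: "From the time measurement criteria are first met for CR/PR (whichever is first recorded) until the first date of recurrent or progressive disease"
- Protocol synopsis: "measured from the time measurement criteria are first met for CR/partial response (PR), whichever is recorded first"
- Protocol 8.2.2: "measured from the time measurement criteria are first met for CR/PR, whichever is recorded first"
- Protocol Appendix 10: "The endpoint is DOR, measured from the time measurement criteria are first met for CR/PR (whichever is first recorded")

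SAP 5.8.2 analyses DOR by Kaplan-Meier (median and rates at fixed months) and counts patients with DOR of at least 4, 6, 8 and 12 months.

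**The concern.** DOR stands above the day-count sentence, has both an event and a censoring date, and is analysed by Kaplan-Meier. It is therefore one of the variables the rule covers. No exception for DOR, and no separate day-count, appears in SAP 4.5.2, in the DOR analysis text of 5.8.2 or in the data conventions of Section 6. The only explicit formula for the endpoint thus conflicts with its definition, and two programmers could produce different DOR values while each following the SAP.

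The error has one direction. Counting from first dose adds the time before the response, so median DOR, the Kaplan-Meier DOR rates and the threshold counts would all be overstated. This would affect Groups 1 to 4 and Group 6, for which DOR is a secondary objective (SAP 1.2.2). Under the event and censoring rules of SAP 4.5.2, which are the same for DOR and PFS among responders, the formula would make each responder's DOR equal to that responder's PFS.

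**Working it through.** The documents give no figure that depends on the DOR origin, so there is nothing to reproduce. The check compares the text and then works out the size of the discrepancy.

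**Origin by variable**

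| Variable | Origin in its SAP definition | Origin in the day-count rule | Agree? |
|---|---|---|---|
| TTR | start of treatment | first treatment | yes |
| PFS | start of treatment | first treatment | yes |
| OS | start of treatment | first treatment | yes |
| DOR | first CR/PR | first treatment | **no** |

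**Algebra.** Day 1 is the first dose.

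- Rule: event or censoring date − first treatment date + 1
- Definition: event or censoring date − first CR/PR date + 1
- Rule minus definition = first CR/PR date − first treatment date = TTR − 1 day

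**Inputs.** SAP 2.3 places tumour assessments at the end of each cycle. Cycles last 56 days in Groups 1, 2 and 4 and 63 days in Groups 3 and 6. The ±3-day window comes from the protocol's schedule tables. The Group 6 imaging row is not legible in the available text, so its scan day is taken from the cycle length and the end-of-cycle rule. One month is 30.4375 days.

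| Response seen at | Groups 1, 2, 4 | Groups 3, 6 |
|---|---|---|
| First scan, earliest in window | day 53: 52 days (1.7 months) | day 60: 59 days (1.9 months) |
| First scan, nominal | day 56: 55 days (1.8 months) | day 63: 62 days (2.0 months) |
| Second scan, nominal | day 112: 111 days (3.6 months) | day 126: 125 days (4.1 months) |

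**Effect on the 6-month count.** Six months is 6 × 30.4375 = 182.625 days. A patient responding on day 63 would reach that row with a true DOR of 182.625 − 62 = 120.6 days (4.0 months). A patient responding on day 56 would reach it at 182.625 − 55 = 127.6 days (4.2 months).

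**One patient (assumed dates).** Response on day 63 and PD on day 189:

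- by definition, 189 − 63 + 1 = 127 days (4.2 months)
- by the rule, 189 − 1 + 1 = 189 days (6.2 months)

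**Share of responders with DOR of at least 6 months.** This assumes exponential DOR with every response on day 63. The medians are assumptions chosen to show a range.

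| True median DOR | By definition | By the rule |
|---|---|---|
| 6 months | 50.0% | 63.3% |
| 12 months | 70.7% | 79.5% |
| 24 months | 84.1% | 89.2% |

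**The case against.** The strongest reply is that this is a drafting slip which the documents largely resolve themselves. The origin of DOR is stated the same way in five places, one of them just above the formula, and a specific endpoint definition normally prevails over a generic convention. SAP 1.2.4, which lists departures from the protocol's statistical section, mentions no change to DOR. Protocol Appendix 10 says the Group 6 methods will match those of Groups 1 to 3, and its Table 20 shows that the primary analysis of those groups had already been run. Nothing suggests that any DOR was computed from first dose, and values identical to PFS in every responder should be caught in checking. DOR is also descriptive, with no test and no multiplicity adjustment.

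Most of this stands, and it limits the point: the effect is conditional and the figures above are illustrative. It does not remove the contradiction. Five consistent definitions show that the rule is the sentence in error; they do not make it correct. A SAP for a pivotal trial should not depend on a programmer recognising which of its statements to disregard for the endpoint it labels key secondary.

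A further objection is that the protocol measures PFS and OS from enrolment while the SAP uses start of treatment. That is a separate question. The correction proposed here concerns DOR only and takes no position on it.

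**Conclusion.** The day-count rule in SAP 4.5.2 is wrong as written for DOR, and for DOR alone among the four variables as the SAP defines them. If applied, it lengthens each responder's DOR by TTR − 1 day: about 2 months for a response at the first scheduled scan, and about 4 months for one at the second. These sizes assume nominal scan days and a minus sign in the formula. If DOR is programmed from first response, the reported results are unaffected and only the text is at fault. The primary ORR analysis, sample size and alpha do not change in either case. This should be fixed, but it does not threaten the trial's primary conclusion.

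**What to change.** Limit the existing sentence to TTR, PFS and OS, show the minus sign if it is missing from the source file, and add a line:

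DOR (days) = date of PD, death or censoring − date of first CR/PR + 1.

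The sponsor should also confirm which origin the existing DOR programs use for every group. The cost is one or two lines of SAP text, with no new data and no change to the primary analysis. If the programs already count from first CR/PR, no output changes; if any count from first dose, the DOR median, Kaplan-Meier rates and threshold counts need to be rerun.

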4.5.3. Exploratory Efficacy Variable

Group 4 (excluding patients enrolled in Germany): ORR based on ¹⁸F-FDG-PET is determined by the proportion of patients with best overall response of complete metabolic response (CMR) or partial metabolic response (PMR) using EORTC criteria (Appendix 9 of the protocol).

4.5.4. Exploratory Biomarker Variables

Biomarker variables for exploratory analyses of association with clinical efficacy endpoints may include:

- [REDACTED]
- [REDACTED]
- [REDACTED]
- [REDACTED]
- [REDACTED]
- [REDACTED]
- [REDACTED]

4.6. Safety Variables

Patient safety will be assessed through the collection of reported adverse events (AEs), clinical laboratory data, vital signs, ECG and physical exam. Unless otherwise noted, the baseline value is defined as the last available value before the first dose of study treatment.

4.6.1. Adverse Events and Serious Adverse Events

The investigator (or designee) will seek information on AEs at each patient contact and record all AEs that occur from the time the informed consent is signed until 105 days (5 half-lives) after

the end of study treatment. After informed consent has been obtained but prior to initiation of study treatment, only the following categories of AEs should be reported on the AE electronic CRF:

- SAEs
- Nonserious AEs associated with a protocol-mandated intervention (eg, AEs related to an invasive procedure such as a biopsy)

Other AEs that occur prior to first treatment should be reported on the medical history CRF.

All AEs after initiation of study treatment and until 105 days (5 half-lives) after the last study treatment, regardless of relationship to study treatment, will be reported on the AE electronic CRF. Additionally, any SAE or other AE of concern that the investigator believes may be related to study treatment and that occurs later than 105 days (5 half-lives) after last study treatment should be reported.

Group 5 patients only: any local ISRs will be reported as AEs in the CRF, as appropriate.

All adverse events are to be coded to a Preferred Term (PT) and associated primary System Organ Class (SOC) according to the latest available version of Medical Dictionary for Regulatory Activities (MedDRA).

An Adverse Event (AE) is any untoward medical occurrence in a patient or clinical investigation patient administered a pharmaceutical product and which does not necessarily have to have a causal relationship with this treatment. A Serious Adverse Event (SAE) is an AE that is classified as serious according to the criteria specified in the protocol.

The severity of AEs (including test findings classified as AEs) will be graded using the National Cancer Institute-Common Terminology Criteria for Adverse Events (NCI-CTCAE) version 4.03. Adverse events not listed in the NCI-CTCAE will be graded according to the following scale:

- 1 (Mild): Mild; asymptomatic or mild symptoms; clinical or diagnostic observations only; intervention not indicated.
- 2 (Moderate): Moderate; minimal, local or noninvasive intervention indicated; limiting age-appropriate instrumental ADL*.
- 3 (Severe): Severe or medically significant but not immediately life threatening; hospitalization or prolongation of hospitalization indicated; disabling; limiting self-care ADL**.
- 4 (Life-threatening): Life-threatening consequences; urgent intervention indicated.
- 5 (Death): Death related to AE.

* Instrumental Activities of Daily Living (ADL) refer to preparing meals, shopping for groceries or clothes, using the telephone, managing money, etc.

** Self-care ADL refers to bathing, dressing and undressing, feeding self, using the toilet, taking medications, and not bedridden.

The relationship of AEs to study drug will be assessed by the investigator and be determined based on protocol specified criteria.

Laboratory results, vital signs, or ECG abnormalities are to be recorded as AEs if they are medically relevant: symptomatic, requiring corrective therapy, leading to treatment discontinuation and/or fulfilling a seriousness criterion.

4.6.2. Adverse Events of Special Interest

An AE of special interest (AESI) must be reported within 24 hours of identification. AEs of special interest for this study include:

- Grade 2 or greater infusion-related reactions
- Grade 2 or greater allergic/hypersensitivity reactions
- Grade 3 immune-related toxicities (irAE)
- Grade 3 or greater ISR for the SC route
- An irAE of any grade in a patient previously treated with a PI 3-K inhibitor

Note: An irAE can occur shortly after the first dose or several months after the last dose of treatment. All AEs of unknown etiology associated with drug exposure should be evaluated to determine possible immune etiology. If an irAE is suspected, efforts should be made to rule out neoplastic, infectious, metabolic, toxin or other etiologic causes prior to labeling an AE as an irAE.

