5.3.2.2. Management of Immune-Related Adverse Events

Adverse events that meet the criteria for irAEs, as noted above in the Investigator's Brochure, should be reported as irAEs in the case report form (CRF). If AEs corresponding to the common terms for irAEs are attributed as NOT related to cemiplimab by the investigator, additional information should be provided to substantiate an alternative attribution (eg, infectious diarrhea).

If not provided at the outset, this information may be requested by immediate edit checks or in subsequent queries. The sponsor may request additional information for any AE that is of a type

known to be potentially immune-related (eg, rash, colitis, elevated transaminases, endocrine events), but is deemed not an irAE by the investigator. Any grade 3 or greater irAE should be reported as an adverse event of special interest (AESI).

The following general principles apply to management of irAEs, unless otherwise specified in [Appendix 4](#):

Grade 1: Continue study treatment with close monitoring and provide symptomatic management

Grade 2: Consider withholding study treatment

Grade 3: Withhold study treatment

Grade 4: Discontinue study treatment

If cemiplimab is held for \leq grade 3 irAE, consider resuming when symptoms and/or laboratory values revert to baseline or \leq grade 1 after corticosteroid taper (typically, to ≤ 10 mg/day prednisone or equivalent).

Permanently discontinue study treatment for:

- Recurrent grade 3 irAEs
- Grade ≥ 3 or recurrent Grade 2 Pneumonitis
- Grade ≥ 3 Hepatitis with AST/ALT $> 5 \times$ ULN or total bilirubin $> 3 \times$ ULN
- Grade ≥ 3 Nephritis with renal dysfunction
- Grade ≥ 3 Uveitis
- Grade ≥ 3 Neurologic toxicity
- Grade ≥ 3 Myocarditis or pericarditis
- Grade ≥ 3 Infusion related reaction
- Confirmed SJS, TEN or DRESS
- Grade ≥ 3 or recurrent Grade 2 events in patients previously treated with idelalisib
- Grade 2 or 3 irAEs persistent for ≥ 12 weeks after the last study treatment (excluding endocrinopathies)
- Requirement for ≥ 10 mg per day prednisone or equivalent lasting ≥ 12 weeks after the last study treatment

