7.2.3. Other Events that Require Accelerated Reporting to the Sponsor

The following events also require reporting to the sponsor (or designee) within 24 hours of learning of the event:

Symptomatic Overdose of Study Drug:

Accidental or intentional overdose of at least 2 times the intended dose of study drug within the intended therapeutic window, if associated with an AE.

Pregnancy:

Although pregnancy is not considered an AE, it is the responsibility of the investigator to report to the sponsor (or designee), within 24 hours of identification, any pregnancy occurring in a female patient or female partner of a male patient, during the study or within 105 days of the last dose of study drug. Any complication of pregnancy affecting a female study patient or female partner of a male study patient, and/or fetus and/or newborn must be reported as an SAE. Outcomes for all pregnancies should be reported to the sponsor.

Adverse Events of Special Interest:

An AESI must be reported within 24 hours of identification. Adverse events of special interest for this study include:

- Grade 2 or greater infusion-related reactions
- Grade 2 or greater allergic/hypersensitivity reactions
- Grade 3 or higher irAEs
- Grade 3 or greater ISR for the SC route
- An irAE of any grade in a patient previously treated with a PI 3-K inhibitor

Note: An irAE can occur shortly after the first dose or several months after the last dose of treatment. All AEs of unknown etiology associated with drug exposure should be evaluated to determine possible immune etiology. If an irAE is suspected, efforts should be made to rule out neoplastic, infectious, metabolic, toxin or other etiologic causes prior to labeling an AE as an irAE.

Refer to the safety reporting guidelines for the reporting procedures to be followed.

If any SAE or unusual AE is judged related to study treatment, and as possible and practical, obtain a blood sample from the patient to permit measurement of plasma drug levels.

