5.9. Analysis of Safety Data

The analysis of safety and tolerance will be performed on the SAF, as defined in Section 3.2.

The safety analysis will be based on the reported AEs and other safety information (clinical laboratory evaluations, vital signs and 12-lead ECG). The analysis will comprise the basis upon which conclusions will be drawn regarding the cemiplimab. The AE of special interest will be determined by the list provided by medical monitors.

Period of observation: The observation period will be divided into three segments: pre-treatment, on-treatment and post-treatment.

- The pretreatment period is defined as the time from signing the ICF to before the first dose of study drug.
- The on-treatment period is defined as the day from the first dose of study drug to 105 days after the last dose of study drug or to follow-up visit, whichever is longer. For patients who started cemiplimab as re-treatment more than 30 days after their last regular cemiplimab treatment, the on-treatment period ends at the earlier day of 105 days after the last regular cemiplimab dose or 1 day before their first dose of cemiplimab re-treatment.
- The post-treatment period is defined as the time starting 1 day after the on-treatment period.

Day 1 is the first day of patient receiving cemiplimab treatment, Day –1 is the day before, and there is no Day 0.

The safety analysis will be concentrated on events that occur during on-treatment period. Events that occur during post-treatment period, or during cemiplimab re-treatment will be listed and summarized if necessary.

The summary of safety results will be presented by group and combined.

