5.9.1. Adverse Events

The verbatim text, the primary system organ class (SOC), and the preferred term (PT) will be displayed in subject listings. Summaries that include frequencies and proportions of patients reporting AEs will include the SOCs and the PTs.

Definitions:

- Pre-treatment AEs are defined as AEs that developed during the pre-treatment period.
- Treatment-emergent AEs (TEAEs) are defined as AEs that developed or worsened during the on-treatment period and any immune-related AEs that occurs any time after the first dose of cemiplimab.
- Post-treatment AEs are defined as AEs that developed or worsened during the post treatment period and are not considered drug related by the investigator.

The focus of adverse event reporting in the CSR will be on TEAEs. For details on handling missing data and partial dates, see Section 6.

Summaries of AEs will include: TEAEs, Treatment related TEAEs, Serious TEAEs, Treatment-related Serious TEAEs, AESI, immune-related AEs, and infusion related AEs. For TEAEs, the following will be summarized:

- The number and proportions of patients reporting at least 1 TEAE, presented by SOC and PT
- TEAEs by severity (CTCAE, version 4.03 grade), presented by SOC and PT
- TEAEs related to treatment, presented by SOC and PT
- TEAEs occurring in $\geq 5\%$ patients, presented by PT
- TEAEs leading to permanent treatment discontinuation, presented by SOC and PT
- TEAEs leading to death, presented by SOC and PT

For each TEAE summary presented by SOC and PT, the summary table will be sorted by decreasing frequency of SOC and PT. For TEAE summary presented by PT, the summary table will be sorted by decreasing frequency of PT.

The irAEs reported by investigator will be summarized. Additionally, irAEs identified by the sponsor will be summarized. All irAEs occurred during the on-treatment and post-treatment period will be included.

For AE listings, the following variables will be displayed:

- Age/Gender
- Verbatim Term, SOC, PT
- AE start date and end date/ongoing (and corresponding study day)
- AE duration
- Relationship to study drug: unrelated or related
- Seriousness (Serious AE or not)
- National Cancer Institute-Common Terminology Criteria for Adverse Events (NCI CTCAE) grade
- Action taken
- Treatment for AE
- Outcome

Counts will be provided for each patient within each SOC and PT. Percentages will be calculated using the number of patients from the SAF in each group.

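### Two SAP safety definitions are too narrow as written: the AESI item for irAEs stops at Grade 3, and a late drug-related, non-immune AE has no label (minor)

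*SAP*

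**What the plan says.** **AESI.** SAP 4.6.2 gives a list in which the irAE item reads "Grade 3 immune-related toxicities (irAE" and the injection-site item reads "Grade 3 or greater ISR for the SC route". The infusion-reaction and hypersensitivity items also run upward, from Grade 2. A final item admits an irAE of any grade, but only after a prior PI 3-K inhibitor. Protocol 7.2.3 has "Grade 3 or higher irAEs", and protocol 5.3.2.2 says "Any grade 3 or greater irAE should be reported as an adverse event of special interest (AESI". For the analysis, SAP 5.9 states: "The AE of special interest will be determined by the list provided by medical monitors". SAP 5.9.1 names AESI among the AE summaries to be produced.

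**AE labels.** In SAP 5.9.1 a TEAE is an AE that begins or worsens in the on-treatment period, together with "any immune-related AEs that occurs any time after the first dose of cemiplimab". The next category reads: "Post-treatment AEs are defined as AEs that developed or worsened during the post treatment period and are not considered drug related by the investigator". Pre-treatment and post-treatment AEs each go into their own listing. For the irAE summaries, "All irAEs occurred during the on-treatment and post-treatment period will be included".

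**Periods.** SAP 5.9 ends the on-treatment period 105 days past the last dose or at the follow-up visit, whichever is later. If re-treatment starts more than 30 days after the last regular dose, the period ends at day 105 or on the day before re-treatment, whichever is earlier. The post-treatment period begins the next day. SAP 5.9 also says that events in the post-treatment period or during re-treatment will be listed, and it sets no relatedness condition.

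**The concern.** The first item looks like a dropped phrase. Every other graded item in the list is open upward, and the SAP's wording is narrower than the protocol's in two places. A programmer who follows SAP 4.6.2 literally would build an AESI table that leaves out life-threatening and fatal irAEs.

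The second item is an inconsistency inside the SAP. The protocol defines a post-treatment period in 9.5.4.1 but no post-treatment AE category, so the relatedness condition comes from the SAP alone. It removes from the post-treatment listing the events attributed to the drug. Those that are immune-related are picked up by the TEAE definition; the rest are picked up by neither definition. At stake are the content of the AESI summary and the completeness of one listing.

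**Working it through.** The documents give no figure to reproduce. The check sets the passages side by side and enumerates the labels.

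**AESI grades.** SAP 4.6.2 has four graded items:

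- infusion-related reactions: Grade 2 and up
- allergic or hypersensitivity reactions: Grade 2 and up
- irAEs: Grade 3
- injection-site reactions by the SC route: Grade 3 and up

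One of the four has no upward extension. The protocol's irAE item covers Grades 3, 4 and 5. The SAP wording covers Grade 3, so 1 of 3 grades is inside and 3 − 1 = 2 are outside, apart from patients with a prior PI 3-K inhibitor.

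**AE labels.** After the first dose, take period (on, post) × drug-related (yes, no) × immune-related (yes, no), which gives 2 × 2 × 2 = 8 combinations. The four on-treatment combinations are all TEAEs. The four post-treatment combinations under SAP 5.9.1 are:

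| Drug-related | Immune-related | TEAE? | Post-treatment AE? |
|---|---|---|---|
| yes | yes | yes | no |
| no | yes | yes | yes |
| no | no | no | yes |
| yes | no | no | no |

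One combination has no label and one has two.

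**Re-treatment.** When it starts more than 30 days after the last regular dose, the on-treatment period has ended by the day before. A drug-related, non-immune AE during re-treatment is therefore not a TEAE. Nor is it a post-treatment AE. If re-treatment counts as part of the post-treatment period, as the period definitions imply, the relatedness clause excludes it. If re-treatment stands apart, as the listing sentence in SAP 5.9 suggests, the event lies outside the post-treatment period. It has no label on either reading. This applies to Groups 1 to 5; Group 6 patients are not eligible for re-treatment (protocol 6.2.2, SAP 2.3).

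**The case against.** The case for leaving this alone is substantial, and much of it stands.

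- **AESI.** SAP 4.6.2 largely repeats the protocol's accelerated-reporting list. For analysis, SAP 5.9 relies on the medical monitors' list, which may already follow the protocol. Grade 4 and 5 irAEs remain in the irAE summaries, which have no grade limit, and in TEAEs by severity; fatal ones also appear in TEAEs leading to death. A reader might infer that high-grade irAEs would go unreported. The documents do not support that. What remains is that the content of the monitors' list is not given, and the SAP ties it neither to 4.6.2 nor to the protocol, so it cannot be shown to repair the wording.
- **Late events.** A reader might infer that late related events are lost. They are not shown to be. SAP 5.9 promises to list post-treatment and re-treatment events whatever their relatedness, AE listings carry the relationship to study drug, and protocol 9.5.4.1 lists and summarizes deaths and other SAEs. This is a gap in labels and in one listing.
- **SAP 4.6.1.** A reader might also see a contradiction with SAP 4.6.1, which still asks for related SAEs and AEs of concern beyond 105 days. That section governs collection and 5.9.1 governs analysis labels. An event that is collected but unlabelled is a gap, not a contradiction.
- **Length of re-treatment.** Protocol 6.2.2 allows up to 108 weeks, and a reader might take this as the size of the problem. It is a window length. It says nothing about how many events are affected, and it does not apply to Group 6.

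**Conclusion.** Both defects are present in the text, and both are minor. Followed as written, SAP 4.6.2 yields an AESI category covering one of the protocol's three irAE grades. SAP 5.9.1 yields a post-treatment listing without drug-related, non-immune events, and double-labels irAEs judged unrelated in that period. The first consequence assumes that the monitors' list follows SAP 4.6.2 literally. The second assumes that the listing is programmed from the 5.9.1 definition and not from the broader sentence in 5.9. The numbers of re-treated patients and of late events are not in the documents, so no effect on the outputs can be calculated. ORR, the main TEAE tables, the irAE summaries and data collection are unaffected.

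**What to change.** - **SAP 4.6.2 and 5.9:** replace the irAE item with the protocol's wording, "Grade 3 or higher irAEs", and state that the medical monitors' list applies this definition.
- **SAP 5.9.1:** delete the closing relatedness clause from the post-treatment AE definition, and exclude irAEs already counted as TEAEs. Leave the TEAE definition as it is.
- **Re-treatment:** list re-treatment AEs separately from off-drug post-treatment AEs, as SAP 5.9 already implies. Without this step, deleting the clause would place events that occur on drug under a post-treatment heading.

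After these changes each of the four combinations has one place: both immune-related ones are TEAEs, and both non-immune ones go to the off-drug post-treatment listing or the re-treatment listing. The cost is a few words in three SAP sections and one listing split into two. The main TEAE tables do not change.
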